6.8 Assessment of Safety

Any patient who receives at least one dose of metformin treatment on this protocol will be evaluable for toxicity via NCI CTCAE v 4.0.

6.9 Assessment of Efficacy

All patients who receive at least 3 months of metformin therapy will be evaluable for assessment of the primary endpoint – response at 6 months.

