4.7 Duration of Metformin Therapy

The planned duration of metformin therapy is 12 months. Metformin treatment will be discontinued early in the following scenarios:

- Progression of disease, as defined by CAH progression to invasive adenocarcinoma or grade 1 EC progression to grade 2 or 3 EC, at any of the standard of care biopsies at 3, 6, and 9 months. In any of these cases, metformin will be discontinued within 3 days of results of the biopsy.
- Unacceptable toxicity as defined by a single grade 3 or higher GI disturbance attributed to metformin, a single grade 4 or higher hypoglycemia episode, 2 or more grade 2 toxicities attributed to metformin, or requirement for a dose below 850 mg once daily.

Response to therapy will be assessed at 3-month intervals. As per standard of care, endometrial biopsies will be performed every 3 months (+/- 2 weeks) to assess histology and grade to determine response. This will be the basis of whether therapy should continue. If the 3 month biopsy demonstrates disease progression, the patient will be removed from protocol directed treatment and followed-up per protocol, and treatment decisions will be at the discretion of the treating physician. Otherwise, therapy will continue through 6 months. If the 6-month or 9-month biopsy demonstrates complete response (complete disease regression) or partial response (partial disease regression), metformin will be continued until 12 months of total therapy is given. If the 6-month or 9-month biopsy demonstrates stable disease, continuation of metformin on study will be at the discretion of the treating physician. Please see the schema (section 4.1) for clarity.

In addition, treatment will be stopped in the setting of:

- Inter-current illness that prevents further administration of treatment
- Pregnancy
- Patient decides to withdraw from study treatment, **OR**
- General or specific changes in the patient's condition render the patient unacceptable for further treatment in the judgment of the investigator.

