8.2 Sample Size, Stopping Rule, and Accrual

The goal accrual is 32 patients (16 CAH, 16 EC) and we expect to enroll 1-2 patients/per month. Our power calculation and analysis will be based on 30 patients, assuming early discontinuation of 2 participants prior to 3 months of treatment. We estimate 18 months to complete accrual.

The primary objective of this study is to compare the CR rate at 6 months to a rate of 50% (the 50% is based on results reported in the meta-analysis referenced earlier, and because a response rate significantly greater than this will be considered clinically meaningful by the investigators). With a combined sample size of 30 evaluable patients with either CAH or grade 1 EC, and assuming a null CR rate of 50% and an alternative of 75%, we will have 80% power to conclude that the CR rate at 6 months is significantly higher than 50% using an exact test for a single proportion with a two-sided α of 0.05. Furthermore, the exact 95% confidence interval for the CR rate at 6 months will have a maximum width of 0.374. This means that the CR rate will be estimated within at least 18.7%. CAH and grade 1 EC represent a spectrum of neoplasia, which is why the two groups are being combined for the primary objective. The CR rate at 6 months will be estimated separately in the CAH and EC groups as a secondary objective.

Sequential boundaries will be used to suspend the trial if excessive toxicity is seen that requires discontinuation of metformin. If the study reaches a stopping boundary, it may be terminated by the PI, or submitted to the DSMC with a description of the toxicities and a rationale for why the study should be continued. At the patient level, metformin will be discontinued if a patient experiences: (1) a single grade 3 or higher metformin-related GI disturbance or grade 4 or higher hypoglycemic episode, or (2) two or more grade 2 side effects considered related to metformin therapy, or (3) if the patient requires a dose less than 850mg once daily. The accrual will be halted if the number of patients discontinuing metformin for one of the reasons above is equal to or exceeds b_n out of n patients who have been followed for toxicity for 3 months. This is a Pocock type stopping

boundary that assumes that a metformin discontinuation rate of 0.25 is acceptable, but anything $>25\%$ is unacceptable. If the true toxicity rate is equal to 0.25, the probability of crossing the boundary is 0.05.

Stopping Rule

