8.3 Data Analysis Plans

An exact test for a single proportion will be used to test the hypothesis that the CR rate at 6 months for the group as a whole is greater than 50%. The CR rates at 6 months for the group as a whole and for the CAH and grade 1 EC patients separately will also be estimated and reported along with exact 95% confidence intervals. Patients who progress at 3 or 6 months will be considered non-responders and will be included in these analyses. Patients who fail to complete 3 months of metformin therapy, for reasons unrelated to disease progression or activity, will not be included. The CR rate at 12 months will also be estimated and the analysis will include all patients who had at least 3 months of metformin therapy.

Patient adherence will be described by the percentage of patients able to adhere to at least 80% of planned metformin doses over the course of treatment. The adherence rate will be estimated and reported along with an exact 95% confidence interval. All patients who initiated treatment on study will be included in this analysis. Adverse events will be described by type and grade using frequency tables.

Changes in Ki-67 from baseline to 6 months will be analyzed using a paired t-test or the Wilcoxon signed-rank test as appropriate. Fisher's exact tests will be used to explore associations between expression (via IHC) of the metformin transporter proteins and key targets of the metformin/mTOR signaling pathway and CR at 6 months. Two-sample t-tests will be used to explore associations between metabolic factors and CR. Correlation coefficients and regression models will be used to explore associations between metabolic factors and metformin concentration levels in tumor tissue. Profiling of metabolites and all associated metabolomic analyses will be conducted by the UNC NORC/Nutrition Research Institute Metabolomics Core.

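### Women who progress before completing 3 months of metformin are non-responders in Section 8.3's 6-month analysis, but fall outside the set in Section 6.9 and the 12-month set in 8.3

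*Combined protocol and SAP*

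**What the plan says.** Three statements define who is analysed for response.

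- **Section 6.9 (Assessment of Efficacy):** "All patients who receive at least 3 months of metformin therapy will be evaluable for assessment of the primary endpoint". Length of metformin exposure is the only criterion, and the reason for stopping plays no part.
- **Section 8.3 (Data Analysis Plans), 6-month rate:** "Patients who progress at 3 or 6 months will be considered non-responders and will be included in these analyses". It adds: "Patients who fail to complete 3 months of metformin therapy, for reasons unrelated to disease progression or activity, will not be included". Short exposure leads to exclusion only when the reason has nothing to do with the disease.
- **Section 8.3, 12-month rate:** "the analysis will include all patients who had at least 3 months of metformin therapy". The exception for disease-related stopping is not repeated, and nothing says how an earlier progressor is scored.

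Two statements in Section 4.7 (Duration of Metformin Therapy) bear on whether a progressor can fall short of 3 months. The first is that "endometrial biopsies will be performed every 3 months (+/- 2 weeks) to assess histology and grade to determine response". The second is that, on progression, "metformin will be discontinued within 3 days of results of the biopsy". Footnote 6 of the Time and Events Table, by contrast, gives 90 days as the shortest metformin treatment.

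**The concern.** A woman whose first follow-up biopsy shows progression, and who stops metformin before 3 months, is treated in three ways. Under 8.3 she counts against the treatment at 6 months. Under 6.9 she is not among the evaluable patients. At 12 months she is not in the set at all.

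The direction is one-sided. Such a woman is a non-responder, so leaving her out cannot lower the CR rate. The trial is open-label and single-arm and is tested against a fixed 50%, so no control group would share the effect. If the sets are not reconciled beforehand, the denominator could be settled after the responses are known.

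**Working it through.** **1. The plan's own figures.** Section 8.2 has 30 evaluable patients, a null rate of 50%, an alternative of 75%, and an exact test at two-sided 0.05. The smallest r with P(X ≥ r | 30, 0.5) ≤ 0.025 is r = 21, with tail 0.0214 and two-sided p = 2 × 0.0214 = 0.043. Power is P(X ≥ 21 | 30, 0.75) = 0.803, which matches the stated 80%. The widest exact 95% interval, at 15/30, runs from 0.313 to 0.687. Its width of 0.374 is also as stated. Neither figure is in dispute.

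**2. Can the case arise?** Take 3 months as 90 days (an assumption). A biopsy two weeks early falls on day 76. Metformin stops after the result, and no turnaround time for follow-up biopsies is given. Let L be the days from biopsy to stopping. Exposure is under 90 days when the biopsy falls before day 90 − L. For an assumed L of 3 to 10 days:

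- biopsy on day 76: 79 to 86 days of metformin, under 90 throughout;
- biopsy on day 84: 87 to 94 days, so it depends on L.

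The case is therefore possible, but only for progression found in the early part of the window.

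**3. Direction.** With x CRs among n patients and k early progressors scored as non-CR, the rate is x/n if they are kept and x/(n − k) if they are dropped. Since x/(n − k) ≥ x/n, dropping them can only raise the rate or, when x = 0, leave it unchanged.

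**4. Effect on the primary test.** The documents give no expected k, so a range is shown. Here p = 2 × P(X ≥ x | n, 0.5), and the 30 under 8.3 include the k early progressors.

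| k assumed | n under 6.9 | Cut-off at that n | p at that cut-off, 6.9 set | Same count over 30, 8.3 set |
|---|---|---|---|---|
| 1 | 29 | 21 | 0.024 | 0.043 |
| 2 | 28 | 20 | 0.036 | 0.099 |
| 3 | 27 | 20 | 0.019 | 0.099 |
| 4 | 26 | 19 | 0.029 | 0.20 |

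With k = 1 the cut-off is 21 in both sets, so significance agrees for every count. For example, 20/29 gives p = 0.061 and 20/30 gives p = 0.099. With k = 2 the cut-offs are 20 and 21, so the sets disagree only at exactly 20 CRs: 20/28 = 71.4% against 20/30 = 66.7%. The chance of exactly 20 CRs among the other 28 is C(28,20) π^20 (1 − π)^8. That is 0.150 at π = 0.75, 0.012 at π = 0.50, and at most 0.165 (at π = 20/28).

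**5. Effect at 12 months.** Take 18 CRs and k = 2. Keeping the two gives 18/30 = 60.0% (exact 95% CI 0.406 to 0.773). Dropping them gives 18/28 = 64.3% (0.441 to 0.814). The difference is 4.3 percentage points, on an endpoint that is estimated and not tested.

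**The case against.** The best reply is that 8.3 is the analysis plan and already settles the primary endpoint. Its exclusion is limited to reasons unrelated to disease, which keeps exactly the woman at issue. Section 6.9 says that all patients with 3 months are evaluable. It does not say that only they are. This largely stands: the 20/28 result needs an analyst to follow 6.9 and set 8.3 aside. Still, 6.9 is the section that defines evaluability for the primary endpoint, and no order of precedence is given. The reply also does not reach the 12-month sentence, where the omission lies within 8.3.

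A second reply is that footnote 6's 90-day minimum shows that a patient stopping at the 3-month biopsy is meant to count as having had 3 months. That may be the intention, and result turnaround narrows the group further. But the footnote does not fit an early biopsy followed by prompt stopping, so those passages need reconciling too.

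A reader might go further and infer any of the following. The documents do not support them.

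- **The primary analysis as planned drops treatment failures.** Read alone, 8.3 keeps progressors in.
- **The 12-month set loses all progressors.** Those who had a full 3 months of metformin stay in, including women who progress at 6 or 9 months.
- **One woman could reverse the primary conclusion.** The k = 1 row shows that she could not.
- **The false-positive rate is badly inflated.** A large figure would need many early failures removed, for instance at the 25% discontinuation rate in the toxicity stopping rule. Early toxicity stops are excluded by 6.9 and 8.3 alike, so they are not part of this conflict.

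**Conclusion.** The inconsistency is real and should be removed before analysis. For the primary endpoint it is a conflict between two sections, one of which already gives a sound rule. For the 12-month rate it is a gap within 8.3: followed literally, the sentence omits known failures.

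The reach is narrow, namely progressors with under 3 months of metformin. The size depends on how many there are, which the documents do not say. With one, primary significance is unaffected. With two, it changes only at exactly 20 CRs (p = 0.099 against 0.036). At 12 months, two such women among 30 move a rate of 60.0% to 64.3%. These are illustrations and not forecasts. They assume that the women are scored as non-CR, which 8.3 states for 6 months but not for 12.

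**What to change.** Bring 6.9 into line with the rule that 8.3 already applies at 6 months. Suggested wording:

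> Patients who receive at least 3 months of metformin, and patients who stop metformin before 3 months because of disease progression or activity, are evaluable for response at 6 months. Patients who progress at or before the 6-month biopsy are non-responders at 6 months.

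In 8.3, use the same set for the 12-month CR rate, and count patients who progressed at or before the 12-month biopsy as non-CR at 12 months.

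The time limits in this wording matter. A blanket rule that anyone who ever progresses is evaluable and a non-responder would score a woman in CR at 6 months who progresses at 9 or 12 months as a 6-month failure, against the endpoint definition in Section 2.4.1. It would also admit women who stopped early for toxicity only if they later progressed, which is selection on outcome.

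Footnote 6's 90-day minimum, the biopsy window and the stopping provision in 4.7 should be reconciled by those responsible for them. This review takes no position on which should change.

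The cost is a few sentences, with no new visits, data or patients. The reported CR rate may be slightly lower. With 30 evaluable patients the cut-off stays at 21 and power at 0.803, so the stated 80% is unchanged.

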6.10 Adherence

All patients who initiate treatment with metformin will be evaluable for missed doses/week to assess the endpoint of adherence to at least 80% of doses over the cumulative course of treatment.

7.0 ADVERSE EVENTS

7.1 Definitions

7.1.1 Adverse Event (AE)

An adverse event (AE) is any untoward medical occurrence (e.g., an abnormal laboratory finding, symptom, or disease temporally associated with the use of a drug) in a patient or clinical investigation subject administered a pharmaceutical product and which does not necessarily have a causal relationship with this treatment. An AE can therefore be any unfavorable and unintended sign (including an abnormal laboratory finding), symptom, or disease temporally associated with the use of a medicinal product, whether or not related to the medicinal product.

Hospitalization for elective surgery or routine clinical procedures that are not the result of an AE (e.g., surgical insertion of central line) need not be considered AEs and should not be recorded as an AE. Disease progression should not be recorded as an AE, unless it is attributable by the investigator to the study therapy.

7.1.2 Suspected Adverse Reaction (SAR)

A suspected adverse reaction (SAR) is any AE for which there is a *reasonable possibility* that the drug is the cause. *Reasonable possibility* means that there is evidence to suggest a causal relationship between the drug and the AE. A suspected adverse reaction implies a lesser degree of certainty about causality than adverse reaction, which means any adverse event caused by a drug.

Causality assessment to a study drug is a medical judgment made in consideration of the following factors: temporal relationship of the AE to study drug exposure, known mechanism of action or side effect profile of study treatment, other recent or concomitant drug exposures, normal clinical course of the disease under investigation, and any other underlying or concurrent medical conditions. Other factors to consider in considering drug as the cause of the AE:

- Single occurrence of an uncommon event known to be strongly associated with drug exposure (e.g., angioedema, hepatic injury, Stevens-Johnson Syndrome)
- One or more occurrences of an event not commonly associated with drug exposure, but otherwise uncommon in the population (e.g., tendon rupture); often more than once occurrence from one or multiple studies would be needed before the sponsor could determine that there is *reasonable possibility* that the drug caused the event.
- An aggregate analysis of specific events observed in a clinical trial that indicates the events occur more frequently in the drug treatment group than in a concurrent or historical control group

7.1.3 Unexpected AE or SAR

An AE or SAR is considered unexpected if the specificity or severity of it is not consistent with the applicable product information (e.g., Investigator's Brochure (IB) for an unapproved investigational product or package insert/summary of product characteristics for an approved product). Unexpected also refers to AEs or SARs that are mentioned in the IB as occurring with a class of drugs or as anticipated from the pharmacological properties of the drug, but are not specifically mentioned as occurring with the particular drug under investigation.

7.1.4 Serious AE or SAR

An AE or SAR is considered serious if, in the view of either the investigator or sponsor, it results in any of the following outcomes:

- Death;
- Is life-threatening (places the subject at immediate risk of death from the event as it occurred);
- Requires inpatient hospitalization (>24 hours) or prolongation of existing hospitalization;*
- Results in congenital anomaly/birth defect;
- Results in a persistent or significant incapacity or substantial disruption of the ability to conduct normal life functions;
- Important medical events that may not result in death, be life-threatening, or require hospitalization may be considered a serious adverse drug experience when, based upon appropriate medical judgment, they may jeopardize the patient or subject and may require medical or surgical intervention to prevent one of the outcomes listed in the definition. For reporting purposes, also consider the occurrences of pregnancy as an event which must be reported as an important medical event.

*Hospitalization for anticipated or protocol specified procedures such as administration of chemotherapy, central line insertion, metastasis interventional therapy, resection of primary tumor, or elective surgery, will not be considered serious adverse events.

Pregnancy that occurs during the study must also be reported as an SAE.

7.2 Documentation of non-serious AEs or SARs

For non-serious AEs or SARs, documentation must begin from day 1 of study treatment and continue through the 30 day follow-up period after treatment is discontinued.

Collected information should be recorded in the Case Report Forms (CRF) for that patient. Please include a description of the event, its severity or toxicity grade, onset and resolved dates (if applicable), and the relationship to the study drug. Documentation should occur at least monthly.

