2.2 Secondary Objectives

- 2.2.1** To estimate the rate of CR at 6 months separately in grade 1 EC and CAH patients receiving metformin + LR-IUD
- 2.2.2** To estimate the rate of CR at 12 months in non-surgical grade 1 EC and CAH patients receiving metformin + LR-IUD
- 2.2.3** To document patient adherence to long-term (≥ 3 months) metformin administration
- 2.2.4** To describe safety of metformin + LR-IUD treatment

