5.3 Adverse Events Associated with Commercial Drug

The most common adverse reactions associated with the LR-IUD is change in menstrual bleeding pattern, abdominal/pelvic pain, and the formation of headache/migraines. As part of standard therapy, patients would be counseled about these possible effects. They will be instructed to call the gynecologic oncology clinic if any concerns arise.

The majority of LR-IUD users experience resolution of such symptoms between 1 – 12 weeks after insertion. In the setting of changes in bleeding pattern, this is most commonly a decrease in heavy bleeding associated with CAH/EC and would be unlikely to require intervention. Abdominal/pelvic pain will be treated with

non-steroidal anti-inflammatory medication or acetaminophen as needed, in over the counter formulations. Headaches and/or migraines that result from the LR-IUD will be similarly treated with non-steroidal anti-inflammatory medication or acetaminophen. Persistent headaches requiring discontinuation of the LR-IUD would be addressed by the primary physician as this would impact standard of care therapy for inoperable CAH/EC.

Pregnancy. Pregnancy is rare with the LR-IUD, with a reported rate of 0.1% for ectopic pregnancy. There have been 390 live births out of 9.9 million LR-IUD users as of 2006.

Uterine Perforation. At the time of placement of the LR-IUD there is a risk of uterine perforation. Correct technique by trained personnel mitigates most of this risk. Perforation can be recognized at the time of insertion or at any time when the cervical os strings are no longer visible. Pregnancy may occur in this setting.

Expulsion. The highest rate of expulsion occurs in the first month after LR-IUD placement and can be up to 4.9%. Risk factors for expulsion include placement by untrained personnel and recent (<6 weeks) pregnancy or abortion.

Please see the package insert for a comprehensive list of adverse events.

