6.0 EVALUATIONS AND ASSESSMENTS

6.1 Time and Events Table

	Screening	Pre-treatment Visit	Month (Mo) 1 Week (Wk) 1	Mo3	Mo6	Mo9	Mo12	Early Termination ²	Final Study Encounter ²
Inclusion/ Exclusion Criteria	X								
History ¹ and Physical	X			X	X	X	X		
Informed Consent	X								
Education of potential side effects		X							
Pregnancy test (serum), if applicable	X ³								
Random (non-fasting) glucose		X						X	
AST/ALT	X				X	X	X	X	
Serum creatinine	X				X	X	X	X	
Cervical cultures ⁴	X								
MRI or Pelvic US ⁵	X								
D&C, LR-IUD insertion		X							
Pregnancy test (urine)	X ³								
Metformin Treatment ⁶									
AE Assessment									
Patient Diary			X			X ⁷		X	
Request tissue	X ⁸								
Endometrial Biopsy				X	X ⁹	X	X		
Blood and urine collection ¹⁰	X			X	X	X	X	X	

Metformin treatment begins D1 of Month 1; continue as per sections 4.3-4.4

Footnotes to Time and Events Table

¹Comprehensive medical history at baseline; thereafter history focused on symptoms and toxicities

²Patients will be followed until final study encounter, which will occur within 30 days of their final endometrial biopsy while on metformin. Metformin is to be stopped the day of the 12-month endometrial biopsy, or the day on which the results of prior biopsies are known, if they indicate disease progression. In the case of ongoing adverse events/serious adverse event, patients will be followed to resolution of the event. If early termination of the study occurs (i.e., prior to 12 months), the patient will be asked to have serum and urine collected, and the patient followed-up until any treatment related adverse events have resolved or returned to baseline. Their standard of care every 3 month (+/- 2 weeks) endometrial biopsy will be performed as scheduled by their physician as per routine care.

³Women of childbearing potential (WOCBP) must have negative urine pregnancy test within 7 days of D1 of treatment; urine pregnancy test (for WOCBP) will be conducted on the day of outpatient surgery as well, per standard of perioperative care.

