6.3 Pre-Treatment

Per standard course of treatment, all women undergoing IUD placement for the treatment of CAH/EC will undergo dilation and curettage (D&C) procedure to confirm histologic diagnosis and for placement of the IUD if deemed necessary by their primary provider. Urine pregnancy test (for women of childbearing age) will be conducted on the day of outpatient surgery as well, per standard of perioperative care at UNC. Final pathology results from the D&C will be reviewed by the principal investigator. The patient will be notified within 3 days of the receipt of results, confirming CAH/grade 1 EC histology, that she is cleared to start study treatment with metformin. This will occur within 30 days of LR-IUD placement. Blood and urine samples will also be collected for correlative studies (see section 6.7). If the patient does not require a D&C, she will have a urine pregnancy test prior to IUD placement as is the standard of care and will start metformin within 30 days of IUD placement.

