7.3 SAEs or Serious SARs

7.3.1 Timing

After informed consent but prior to initiation of study medications, only SAEs caused by a protocol-mandated intervention will be collected (e.g. SAEs related to invasive procedures such as biopsies, medication washout, or no treatment run-in).

For any other experience or condition that meets the definition of an SAE or a serious SAR, recording of the event must begin from day 1 of study treatment and continue through the 30 day follow-up period after treatment is discontinued.

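### Adverse-event recording starts at the first metformin dose, so LR-IUD events in the gap after placement (up to 30 days) can be missing from the safety description of the combination

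*Combined protocol and SAP*

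**What the plan says.** The safety objective in section 2.2.4 covers the combination: "To describe safety of metformin + LR-IUD treatment".

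Recording starts later than exposure to the device:

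- **Non-serious events (7.2):** "documentation must begin from day 1 of study treatment and continue through the 30 day follow-up period after treatment is discontinued". The same section asks for onset and resolution dates, grade and relationship to the study drug for each recorded event.
- **SAEs (7.3.1):** in general, "recording of the event must begin from day 1 of study treatment". Between consent and that day there is one exception: "prior to initiation of study medications, only SAEs caused by a protocol-mandated intervention will be collected".
- **Day 1:** the Time and Events Table (6.1) states "Metformin treatment begins D1 of Month 1". Sections 6.3 and 6.4.1 also tie study treatment and day 1 to metformin.
- **Enrolment and the gap:** section 4.1 enrols women before D&C and LR-IUD placement. In section 6.3 a woman who needs no D&C "will start metformin within 30 days of IUD placement". The same section sets a 30-day limit after D&C, and section 4.2 gives 30 days for placement in clinic. Section 4.1, however, gives one week.

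Section 5.3 locates several device risks early. Perforation risk arises at placement. On expulsion it says "The highest rate of expulsion occurs in the first month after LR-IUD placement and can be up to 4.9" per cent. Bleeding changes, pain and headache mostly settle over 1 to 12 weeks.

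**The concern.** The objective concerns two components, but the recording window is set by one of them. The device goes in first, and the protocol places its characteristic complications at insertion or in the following weeks. A site that follows sections 7.2 and 7.3.1 exactly need not enter a non-serious device event that begins and ends before the first metformin dose.

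No other scheduled step clearly fills the gap. Under the footnotes to section 6.1, the first AE assessment comes one week after metformin starts, and the calls ask about metformin side effects. Section 7.2 gives no rule for events with onset before day 1 and requires attribution to the study drug only. Section 6.8 makes a woman evaluable for toxicity only after a metformin dose. A woman who has a device complication and never starts metformin is therefore outside the safety set.

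At stake is a descriptive safety table that would be read as the profile of metformin + LR-IUD but could under-report the early device part. The shortfall would grow with the delay before metformin.

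**Working it through.** The plan states no figure on this point, so there is nothing to reproduce. The check sets the dates side by side and then sizes the gap.

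**Step 1: timeline for an enrolled woman.**

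| Event | Timing | Source |
|---|---|---|
| Enrolment | before placement | 4.1 |
| LR-IUD placement | day 0 | 4.2, 6.3 |
| Metformin day 1; AE and general SAE recording begins | up to 30 days after placement (4.2, 6.3) or up to 7 days (4.1) | 6.1, 7.2, 7.3.1 |
| First AE call | one week after metformin starts | 6.1 footnotes |

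The period without required non-serious AE entry is the interval from placement to metformin day 1: up to 30 days on one set of passages, up to 7 on the other.

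**Step 2: does the SAE exception close it?** Before metformin, "only SAEs caused by a protocol-mandated intervention will be collected". Two readings are possible.

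- *Not collected:* section 4.1 calls D&C and device placement standard of care that enrolment does not alter, and section 4.2 says D&C is not part of the study.
- *Collected:* section 7.3.1 names biopsies as an example of what is captured. Follow-up biopsies in this protocol are also standard of care (4.6.1), and insertion has its own row in the Time and Events Table.

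The text does not settle this for serious events. On neither reading does the exception reach non-serious events.

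**Step 3: size, using expulsion.** Inputs are 32 women (8.2) and 4.9% (5.3). Assumptions: 4.9% is the cumulative 30-day risk, the hazard is constant over those 30 days, and all women have the same gap g.

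Risk before day 1 = 1 − (1 − 0.049)^(g/30). Expected number = 32 × that risk. Chance of at least one = 1 − (1 − risk)^32.

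| Gap g | Share of first 30 days | Risk before day 1 | Expected in 32 | P(at least one) |
|---|---|---|---|---|
| 0 | 0% | 0 | 0 | 0 |
| 7 days | 7/30 = 23% | 0.0117 | 0.37 | 0.31 |
| 14 days | 14/30 = 47% | 0.0232 | 0.74 | 0.53 |
| 30 days | 30/30 = 100% | 0.0490 | 32 × 0.049 = 1.57 | 0.80 |

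**Step 4: sensitivity.** The 4.9% is an upper figure. For a 30-day gap at lower first-month risks:

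| Risk | Expected in 32 | P(at least one) |
|---|---|---|
| 1% | 0.32 | 0.28 |
| 2% | 0.64 | 0.48 |
| 3% | 0.96 | 0.62 |

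The constant hazard matters for the shorter gaps. If expulsions cluster soon after placement, a 7- or 14-day gap misses more than the table shows, but at 4.9% never more than 1.57. The documents give no finer timing.

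**The case against.** The strongest reply is that metformin is the investigational agent and the device is given regardless of the study. Combined exposure begins at metformin day 1, so a window from that day is a defensible reading of a combination safety objective. Symptoms lasting beyond day 1 are still present when recording starts, and section 5.3 notes that a perforation may be recognised well after insertion. The affected endpoint is descriptive. The gap may also be short: section 4.1 says one week, and section 4.2 has D&C results read, and the patient told she may start, within 7 days of the procedure.

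Much of this stands and limits the consequence. It does not remove the point. Sections 4.2 and 6.3 allow 30 days, the objective names the device, and an event that resolves before day 1 has no required entry even when the gap is short.

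Three stronger readings are tempting, but the documents do not support them:

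- **Device symptoms lack onset dates, are blamed on metformin and push the trial towards the section 8.2 boundary.** Section 7.2 already requires onset dates and relationship to study drug. The grade 2 criterion in sections 4.4 and 8.2 counts only events judged related to metformin, and section 7.1.2 has that judgement weigh timing and other exposures. Misattribution is conceivable but not shown.
- **Serious insertion events are definitely excluded.** Step 2 shows that the text is ambiguous.
- **The window lets women who have lost the device be analysed as treated with the combination.** Section 6.9 does define efficacy evaluability by metformin duration alone, but that is a question of tracking device status. The AE start date does not create it.

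**Conclusion.** The point holds in a limited form. As written, AE recording can omit non-serious LR-IUD events between placement and metformin day 1, and the status of serious insertion events is unclear. Objective 2.2.4 can therefore understate early device events.

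For expulsion, at the protocol's upper figure, the expected shortfall among 32 women is about 0.4 for a 7-day gap, 0.7 for 14 days and 1.6 for 30 days. For a 30-day gap at 1% to 3% risk it is 0.3 to 1.0. These figures rest on reading 4.9% as the first-month risk, on a constant hazard and on a common gap. They are also ceilings in one respect: an expulsion before day 1 may still be noticed and entered later, although nothing requires it.

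A reader might infer that the whole first month is lost for every woman. That would need every woman to start on day 30, and section 4.1 points to a much shorter gap. The primary comparison of the 6-month CR rate with 50% does not use these data and is unaffected.

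**What to change.** - **7.2 and 7.3.1:** collect LR-IUD- and insertion-related AEs and SAEs, including expulsion or removal, from the day of placement for every enrolled woman. This also settles whether serious insertion events are collected.
- **Source of the data:** for women who start metformin, ask retrospectively at the existing week 1 call. With a 30-day gap that call comes about 30 + 7 = 37 days after placement, so recall should be checked against the clinical record. Women who never start have no such call, and their events must come from the clinical record.
- **eCRF:** add a device/procedure attribution field beside the existing study-drug relationship field.
- **8.3:** tabulate events from placement to metformin day 1 separately from on-metformin events.
- **6.8:** keep metformin toxicity evaluability at one or more doses, and list device events in women who never start metformin separately.
- **4.1 against 4.2 and 6.3:** reconcile the stated interval between placement and metformin, since it fixes the length of the gap.

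The cost is a few amended sentences, a matching note in the Time and Events Table, the eCRF changes and some record abstraction. No new visit is needed. The downside is a few more AE entries and a slightly less favourable reported safety profile. If the sponsor prefers not to collect these events, objective 2.2.4 should be narrowed to the period from metformin start, so that the table is not read as covering the device from placement.
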